Official Title of the study: The Effect of Remote Ischemic Preconditioning in Living Donor Hepatectomy: a randomized clinical trial

NCT number : NCT03386435

IRB approval date: 1th August 2015

Introduction

Liver transplantation(LT) is the gold standard treatment for patients with end-stage liver disease. In light of advancements in surgical techniques, immunosuppressive agents, and perioperative critical care, the overall 3-year survival of patients undergoing LT has exceeded 80%. Despite its outstanding success, LT still entails certain complications including ischemia-reperfusion injury (IRI).

IRI occurs when the blood supply to an organ or tissue is temporarily cut-off and then restored, and it is well-known as an underlying cause of primary non-function, biliary complications, and eventual graft loss after LT. Despite many attempts to ameliorate hepatic IRI, no definitive therapies have been established. In addition, the mechanisms of IRI remain largely unclear.

Remote ischemic preconditioning (RIPC) is a novel and simple therapeutic method to lessen the harmful effects of IRI. RIPC indicate that brief episodes of ischemia with intermittent reperfusion are introduced at a remote site, leading to systemic protection against subsequent insults as evinced on kidney, heart, liver, and other tissues. While RIPC has been shown to reduce hepatic IRI in several small animal studies, the beneficial effects of RIPC in hepatic IRI have been inconsistent. By far, the majority of RIPC studies on hepatic IRI have been animal studies; hence, there are limitations relating to the lack of human clinical trials.

Therefore, our aim was to assess the effects of RIPC on postoperative liver function in living donor hepatectomy.

Study Protocol

Study design and ethical approval

For the donors, the single-center, double-blinded, randomized controlled study was approved by the institutional review board of the Asan Medical Center (2015-0851) and registered with ClinicalTrials.gov (NCT03386435). We collected and analyzed the data in accordance with the ethical standards set in the 1964 Declaration of Helsinki and its amendments.

Participants

For the donor group, adult (aged 18-60 years) liver donors scheduled for elective donor right hepatectomy from August 2016 to July 2017 at Asan Medical Center in Seoul, Korea, were screened for eligibility. Total 160 participants were assessed for eligibility and randomly assigned to either the RIPC group (n=80) or the control group (n=80). 12 donors whose surgical plan changed unexpectedly from open right hepatectomy to other than open right hepatectomy (e.g., laparoscopic right lobectomy [n=9], left lobectomy [n=2], and right posterior segmentectomy [n=1]) were dropped out of the study. The remaining 148 donors (RIPC group [n=75] and control group [n=73]) were analyzed. For randomization, random computer-generated numbers were stored in sealed envelopes that were opened following the induction of anesthesia by an anesthesia nurse who was unaware of the study.

Intervention

After induction of anesthesia and before skin incision, we performed RIPC. The protocol involves 3 cycles of 5-minute inflation of a blood pressure cuff to 200 mm Hg to one upper arm, followed by 5-minute reperfusion with the cuff deflated. In the control group, the same maneuver was applied but without cuff inflation. All interventions were performed by the

anesthetic nurses who were not involved in the study.

Outcomes

In donors, plasma concentrations of AST and alanine aminotransferase (ALT) were measured daily during the first postoperative week to assess the extent of hepatocellular damage. The postoperative liver regeneration index (LRI) at postoperative 1 month and the incidence of delayed recovery of hepatic function (DRHF) were used as surrogate parameters indicating the possible benefits of RIPC. The LRI was defined as $[(V_{LR} - V_{FLR})/V_{FLR}] \times 100$, where V_{LR} is the volume of the liver remnant and V_{FLR} is the volume of the future liver remnant. Liver volume was calculated by CT volumetry using 3-mm-thick dynamic CT images. The graft weight was subtracted from the total liver volume to define the future liver remnant. DRHF was defined based on a proposal by the International Study Group of Liver Surgery, as follows: an impaired ability of the liver to maintain its synthetic, excretory, and detoxifying functions, which are characterized by an increased PT INR and concomitant hyperbilirubinemia (considering the normal limits of the local laboratory) on or after postoperative day 5. The normal upper limits of PT and bilirubin in our institutional laboratory were 1.30 INR and 1.2 mg/dL, respectively. If either the PT INR or serum bilirubin concentration was preoperatively elevated, DRHF was defined by an increasing PT INR and increasing serum bilirubin concentration on or after postoperative day 5 (compared with the values of the previous day).

Statistical analysis plan

Between-group differences in preoperative and intraoperative characteristics and postoperative outcomes were compared using the Chi-square test or Fisher exact test for categorical variables and the Student *t* test or Mann-Whitney U test for continuous variables,

as appropriate. $P < 0.05$ was considered statistically significant. SPSS 23 (IBM Corp., Armonk, NY, USA) software was used for all statistical analyses.

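### AST and ALT are compared after surgery with no preoperative value tied to the endpoint; the test is valid, but prespecified baseline adjustment could make it more precise

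*Combined protocol and SAP*

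**What the plan says.** **Enzyme outcome (Study Protocol, Outcomes).** One sentence defines it: "plasma concentrations of AST and alanine aminotransferase (ALT) were measured daily during the first postoperative week to assess the extent of hepatocellular damage". No preoperative AST or ALT is named there, nor any change from baseline, single day or weekly summary.

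**Other outcomes (same section).** Both use preoperative information in some way. The liver regeneration index is scaled to the remnant volume expected after resection. Delayed recovery of hepatic function switches to a different rule in one situation: "If either the PT INR or serum bilirubin concentration was preoperatively elevated".

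**Analysis (Statistical analysis plan).** One sentence covers baseline and outcome comparisons alike: "Between-group differences in preoperative and intraoperative characteristics and postoperative outcomes were compared using the Chi-square test or Fisher exact test for categorical variables". Measured quantities such as enzyme levels get an unadjusted choice of two tests, namely "the Student *t* test or Mann-Whitney U test for continuous variables". The threshold is 0.05. There is no covariate, change score or repeated-measures model, and the preoperative characteristics are not listed.

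**Numbers and timing (Participants; Intervention).** 160 donors were randomised, 80 per group. "The remaining 148 donors (RIPC group [n=75] and control group [n=73]) were analyzed". Allocation envelopes were opened after induction of anaesthesia, and the cuff cycles came after induction and before incision.

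**The concern.** AST and ALT are the plan's measures of liver-cell damage, and they are the outcomes with no preoperative information attached. Donors may enter surgery with different enzyme levels. To the extent that those levels predict postoperative levels, two things follow. The standard error of the group difference includes variation that has nothing to do with surgery or with preconditioning. And in the one randomisation that actually took place, a chance difference in preoperative enzymes moves the estimated effect.

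The plan's only stated handling of preoperative differences is a between-group test. Such a test neither adjusts the outcome nor adds precision. Because the documents contain no sample-size or power calculation, nothing shows that 148 donors give precision to spare.

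**Working it through.** **Inputs from the documents.** 75 and 73 donors analysed (75 + 73 = 148 = 160 − 12); threshold 0.05; unadjusted two-sample tests.

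**Assumptions.** Two-sided testing, since sidedness is not stated. Outcome and baseline on a scale where each has SD 1 (for enzymes, the log scale), and a t test as the unadjusted comparator. The correlation r between baseline and postoperative value is not in the documents and is varied. There is no design figure in the plan to reproduce.

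**Step 1: standard error of the unadjusted difference.**
SE = √(1/75 + 1/73) = 0.1644 SD.

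**Step 2: benchmark effect.** The difference detected with 80% power is (1.960 + 0.842) × 0.1644 = 0.461 SD. It is back-solved from the sample size, and is not an effect that the plan claims.

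**Step 3: gain from ANCOVA.** The variance is multiplied by 1 − r². The equivalent increase in donors is 1/(1 − r²) − 1. The detectable difference is 0.461 × √(1 − r²). Power at 0.461 SD is Φ(2.802/√(1 − r²) − 1.960).

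| Assumed r | Variance reduction | Equivalent extra donors | Detectable difference (SD) | Power at 0.461 SD |
|---|---|---|---|---|
| 0 | 0% | 0% | 0.461 | 80.0% |
| 0.1 | 1% | 1% | 0.458 | 80.4% |
| 0.2 | 4% | 4% | 0.451 | 81.6% |
| 0.3 | 9% | 10% | 0.439 | 83.6% |
| 0.5 | 25% | 33% | 0.399 | 89.9% |

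These figures ignore the one residual degree of freedom that the covariate uses (146 becomes 145).

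**Step 4: size of a chance imbalance.** The baseline difference between arms also has SE 0.1644 SD, so its 95% limits are ±1.96 × 0.1644 = ±0.32 SD. The part that reaches the outcome is r times the imbalance. At the limit this is 0.03 SD for r = 0.1, 0.10 SD for r = 0.3 and 0.16 SD for r = 0.5.

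**Step 5: validity of the planned test.** The unadjusted t test was simulated under no effect, with 20,000 runs at each of r = 0, 0.3, 0.5 and 0.7. Type I error lay between 4.9% and 5.3%, and the mean bias was at most 0.002 SD. The standard error in step 1 already covers the variation in step 4.

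**Step 6: why not a change score.** With equal SDs, the variance of a change score is 2(1 − r) times that of the raw value. At r = 0.3 this is 1.4, and power falls to 65.8%. At r = 0.5 it equals the unadjusted test (80.0%). Subtracting the baseline would therefore make matters worse at any r below 0.5.

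**The case against.** The strongest reply is that this is a choice about efficiency and not a fault in the analysis. Much of that stands.

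- **Bias.** A reader might infer that leaving out the baseline biases the comparison. The documents do not support that. Allocation used computer-generated numbers in sealed envelopes opened after induction, so differences present before the cuff arise by chance. The 12 exclusions after randomisation (80 − 75 = 5 and 80 − 73 = 7) raise a separate question.
- **No preoperative enzymes.** A reader might also infer that AST and ALT were never measured before surgery, or were measured and used only in a baseline significance test. Neither is stated. The unlisted preoperative characteristics may include them. The definition of delayed recovery shows only that preoperative INR and bilirubin were known.
- **Full carry-over.** It is tempting to say that an imbalance passes straight into the result, or that a high starting value raises every later one. Only the fraction r carries over, and r may differ by postoperative day.
- **Consistency with the other outcomes.** The remnant volume is a denominator, and the alternative rule for delayed recovery compares with the previous day's values. Neither is a covariate adjustment, so they set no standard that AST and ALT fail.
- **Size.** At r of 0.2 to 0.3 the gain is about 2 to 4 points of power. Only at r around 0.5 does it become material, and nothing in the documents says which value applies.

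What the reply does not remove is that the plan leaves the use of a preoperative enzyme value unstated, although any value taken before induction would precede both allocation and treatment.

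**Conclusion.** The point holds as a minor improvement. The planned AST and ALT comparison is valid. It leaves in the result between-donor variance that could be removed, and it is sensitive to chance imbalance. The variance reduction available is 4%, 9% or 25% at an assumed r of 0.2, 0.3 or 0.5, and negligible near zero.

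This rests on two things that the documents do not settle: the correlation, and whether preoperative AST and ALT were recorded at all. It supports no claim that the trial's enzyme result is biased or its error rate wrong.

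**What to change.** If preoperative AST and ALT were recorded alongside the preoperative INR and bilirubin (an assumption to confirm), replace the raw two-sample test for these enzymes as follows.

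1. Name the last AST and the last ALT before induction as the baseline in both arms.
2. Say which postoperative values enter the analysis. Either name one summary, for example the peak over days 1 to 7, or use all days in a repeated-measures model. The plan names neither, and the adjusted model cannot be run until it does.
3. Compare the arms on log AST and log ALT by ANCOVA, with the log baseline of the same enzyme as covariate. Do not use a change score.
4. Do not rely on a baseline significance test to deal with imbalance.
5. State a rule for a missing baseline, such as imputing the mean pooled over both arms.

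**Cost.** A few sentences in the Statistical analysis plan, one degree of freedom per model and, if the values exist, no new blood sample. If they do not exist, the adjustment cannot be made and the unadjusted comparison stands.

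**Status.** The text already reports who was analysed. An adjusted analysis not specified before unblinding must be labelled post hoc and shown beside the unadjusted one.

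### LRI is compared by an unadjusted two-sample test; ANCOVA on V_FLR, already held as its denominator, could recover precision at almost no cost

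*Combined protocol and SAP*

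**What the plan says.** The Outcomes section names "The postoperative liver regeneration index (LRI) at postoperative 1 month", together with delayed recovery of hepatic function, as the surrogate measures of benefit. No outcome is labelled primary. LRI is defined as 100 × (V_LR − V_FLR)/V_FLR. On the denominator, the section says: "The graft weight was subtracted from the total liver volume to define the future liver remnant".

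The Statistical analysis plan has one rule for all comparisons: "Between-group differences in preoperative and intraoperative characteristics and postoperative outcomes were compared using" a chi-square or Fisher test for categorical variables, and a Student t test or "Mann-Whitney U test for continuous variables". It names no covariate and no regression model. The documents contain no sample-size calculation, effect size, SD or correlation.

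On timing, the Participants section says the allocations were "stored in sealed envelopes that were opened following the induction of anesthesia", and the Intervention section says: "After induction of anesthesia and before skin incision, we performed RIPC". The Participants section also gives the final count: "The remaining 148 donors (RIPC group [n=75] and control group [n=73]) were analyzed".

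**The concern.** Dividing by V_FLR is a baseline adjustment with its coefficient fixed in advance. On the log scale, log(V_LR/V_FLR) = log V_LR − log V_FLR, which sets the slope of 1-month volume on V_FLR at exactly 1. If donors with small remnants regrow proportionally more, the true slope is below 1. LRI is then negatively correlated with V_FLR, and that variation enters the test as noise. Error in V_FLR also passes straight into the ratio. ANCOVA estimates the slope from the data instead of fixing it.

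What is at stake is precision, not bias. The planned test could miss a regeneration effect that the same donors could show. With no primary outcome declared and LRI one of two surrogate measures of benefit, that could affect the trial's conclusion.

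A smaller, separate point is that V_FLR subtracts a weight (g) from a CT volume (mL) with no stated conversion. This mainly shifts the reported LRI level in both arms.

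**Working it through.** **Inputs from the documents.** 80 + 80 = 160 randomised; 9 + 2 + 1 = 12 dropped; 160 − 12 = 148 = 75 + 73 analysed. Significance level 0.05, taken as two-sided. There is no design figure to reproduce.

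**Assumed inputs.** 1-month volume 6% larger under RIPC (log 1.06 = 0.0583); V_FLR CV 20% (log SD 0.198); residual CV 13% (log SD 0.1295); an LRI for all 148 donors. Model: log V_LR = a + b·log V_FLR + 0.0583·treatment + error.

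**Formulas.** √(1/75 + 1/73) = 0.1644.

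- ANCOVA: 0.0583/(0.1295 × 0.1644) = 2.74, and Φ(2.74 − 1.96) gives power of about 78%, whatever b is.
- Log ratio V_LR/V_FLR: SD = √(0.1295² + (1−b)² × 0.198²). At b = 0.4 this is 0.176, so 0.0583/(0.176 × 0.1644) ≈ 2.02 and power is about 52%.
- Variance ratio, log ratio to ANCOVA: 1 + (1−b)² × (0.198/0.1295)².

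**Simulation** (20,000 trials per setting; 3,000 for Mann-Whitney). Repeat runs of the t test and ANCOVA columns moved by no more than about one point:

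| Slope b | Variance ratio | t test on LRI | Mann-Whitney on LRI | ANCOVA | With 10% error in V_FLR: t test v ANCOVA |
|---|---|---|---|---|---|
| 0.4 | 1.84 | 51% | 50% | 77% | 41% v 75% |
| 0.6 | 1.37 | 63% | 61% | 77% | 49% v 71% |
| 0.8 | 1.09 | 73% | 72% | 77% | 55% v 66% |
| 1.0 | 1.00 | 77% | 76% | 77% | 58% v 61% |

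Null rejection was 4.6–5.3% for all methods, so no method's validity is in question.

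**Cost and gain without a growth model.** With N = 148 and r the correlation of LRI with V_FLR, ANCOVA multiplies the variance by (1 − r²)(N − 3)/(N − 4). Take an effect that gives 80% unadjusted power, (1.96 + 0.84) × 0.1644 = 0.461 SD:

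- r = 0: variance × 1.007, CI width × 1.0035, power 79.7%
- r = 0.3: variance × 0.916, CI width × 0.957, power 83.3%
- r = 0.5: variance × 0.755, CI width × 0.869, power 89.7%
- r = 0.7: variance × 0.514, CI width × 0.717, power 97.4%

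Break-even is at r = √(1 − 144/145) ≈ 0.08.

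**Timing of the covariate.** Graft weight exists only after the graft has been removed, so V_FLR is not strictly a pre-randomisation quantity. Preoperative total liver volume is. As the sole covariate it does worse: with an assumed total-volume CV of 15% and remnant fraction 40% (SD 5 points), power is 72%, 65%, 57% and 49% at slopes 0.4 to 1.0, against about 77–78% with log V_FLR.

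**Units.** With an assumed total of 1200 mL, graft 700 g and V_LR 900 mL, LRI = 900/(1200 − 700k) − 1. That is 68%, 80%, 94% and 109% at k = 0.95, 1.00, 1.05 and 1.10 mL per g. The comparison moves less: at slope 0.8, power of the LRI t test goes from 75% to 72% across that range (remnant-fraction SD 3 points), or from 75% to 66% (SD 5 points).

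**The case against.** The strongest reply is that nothing is wrong. The test is valid, LRI already divides by V_FLR, and only non-proportional growth or error in V_FLR leaves anything to gain. That is correct, and it makes this a point of efficiency.

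The size of the gain also depends on the inputs. With V_FLR log SD 0.10 and residual 0.129, the t test and ANCOVA give 73% v 77% at slope 0.6 and 77% v 78% at slope 0.8. With V_FLR log SD 0.15 and residual 0.20, they give 40% v 42% and 41% v 42%. Gains of 1 to 5 points are therefore as compatible with the documents as the 26 points at slope 0.4. This stands: the gain is unknown. In none of these settings was ANCOVA materially worse.

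Two objections concern the remedy.

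- **Graft weight is obtained after RIPC.** True, but LRI contains the same graft weight, so the planned test shares the exposure. The total-volume sensitivity analysis can be weaker than the planned test when growth is near proportional (57% v 74% at slope 0.8, 50% v 78% at slope 1.0). A non-significant result there would not contradict the main model.
- **The endpoint changes.** Only in scale. With log V_FLR in the model, the treatment coefficient is the same whether the outcome is log V_LR or log(V_LR/V_FLR), and the latter is log(1 + LRI/100).

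Finally, the text reads as written after analysis, and it does not say that all 148 donors had a 1-month CT. Both points limit what the change can now deliver.

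**Conclusion.** The point holds as an improvement in precision, not as an error or a source of bias. The planned comparison uses V_FLR only as a divisor, although V_FLR must exist for every donor with an LRI. Adjusting for it costs at most one degree of freedom and about 0.35% in interval width. The gain runs from nothing (slope 1, no error in V_FLR) to 26 power points (slope 0.4), or 34 with 10% error in V_FLR, under the assumed 6% effect and CVs of 20% and 13%. Confidence is medium because the documents supply none of these inputs. The case for the change rests on the asymmetry between cost and possible gain, not on any one power figure. The unit conversion is secondary.

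**What to change.** - Analyse log V_LR at 1 month by ANCOVA with treatment and log V_FLR. Report the ratio of remnant volumes with its 95% CI, and keep LRI as a descriptive display.
- Because 148 donors are already reported as analysed, label this a supporting analysis if the results have been seen.
- Add a sensitivity analysis with preoperative CT total liver volume as covariate. It should not be the only adjusted analysis.
- Show LRI over a range of mL-per-g factors as a sensitivity display. No new CT segmentation is needed.
- Optional: AST and ALT "were measured daily during the first postoperative week"; preoperative values are not documented. If they are held, adjust the log postoperative values for them. Starting from 80% power, dividing the noncentrality by √(1 − r²) gives 80.4%, 83.6% and 89.9% at r = 0.1, 0.3 and 0.5.

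The cost is SAP wording and one linear model in the software already named, on volumes already needed to compute LRI. It needs no new donors, visits, scans or image reading.

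### Must the SAP fix in advance how a week of daily AST and ALT values becomes one comparison per enzyme?

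*Combined protocol and SAP*

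**What the plan says.** The Outcomes section says that AST and ALT "were measured daily during the first postoperative week to assess the extent of hepatocellular damage". That gives up to seven values per enzyme per donor, although the exact days are not listed.

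The Statistical analysis plan is one paragraph. It opens "Between-group differences in preoperative and intraoperative characteristics and postoperative outcomes were compared", and then names the "Chi-square test or Fisher exact test for categorical variables" and the Student t test or "Mann-Whitney U test for continuous variables", each to be used where suitable. A P value below 0.05 "was considered statistically significant". The same paragraph covers baseline, intraoperative and postoperative variables alike. It has no separate provision for repeated measurements, multiplicity, effect estimates or confidence intervals, and no outcome is labelled primary.

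The Participants section gives the analysis set: "The remaining 148 donors (RIPC group [n=75] and control group [n=73]) were analyzed".

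**The concern.** A t test or Mann-Whitney test needs one number per donor, and the plan does not say which of the daily values, or which summary of them, that number is. Day 1, the peak, the area under the curve, the week mean, or every day in turn would all fit the wording, and they need not agree. AST and ALT are the outcomes listed first and are the stated measure of hepatocellular damage, and no primary outcome elsewhere settles the matter.

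Two things would be at stake. If every day were tested at 0.05 and any significant day were taken as evidence of benefit, the false-positive rate per enzyme would exceed 5%. In the other direction, a non-significant result given only as a P value might be read as showing no effect when the data are too imprecise for that.

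**Working it through.** **Inputs.** From the document: 75 and 73 donors (Participants) and the 0.05 threshold (Statistical analysis plan). Assumed: two-sided tests, seven daily values per enzyme, equal SDs across days, and between-day correlation of 0.5, 0.7 or 0.9, either equal for all pairs of days or decaying as AR(1). The document gives no SD, correlation, target difference or power, so there is no stated figure to reproduce.

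**1. One comparison per enzyme.** If one summary per donor is tested, the error rate is 5% per enzyme. Over two enzymes it is 1 − 0.95² = 9.75% if they are independent. By simulation it is 8.4% or 7.1% at a between-enzyme correlation of 0.7 or 0.9.

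**2. Every day tested, any significant day counted.** With seven independent tests, 1 − 0.95⁷ = 30.2%. By simulation (400,000 draws of seven correlated normals, any |z| > 1.96), at correlation 0.5/0.7/0.9:

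- equal correlation: 22.9/17.8/11.4%
- AR(1): 26.8/22.5/14.7%

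Hence the range of 11-27%. It depends both on the assumed correlations and on an any-day rule that appears nowhere in the document.

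**3. Would a named week mean be better?** The standard error of a difference in SD units is √(1/75 + 1/73) = 0.1644. The difference detectable on a single day with 80% power (noncentral t, 146 df) is 0.464 SD. With equal correlation ρ, the variance of a seven-day mean relative to one day is (1 + 6ρ)/7 = 0.571/0.743/0.914. The detectable constant effect is therefore 0.464 × √variance = 0.351/0.400/0.443 SD, which is little gain at high correlation.

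If a 0.464 SD effect is present on only three of the seven days, the week mean sees 0.464 × 3/7 = 0.199 SD. Dividing by √variance gives 0.263/0.231/0.208 of its own SD.

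Power at 0.05 per enzyme, equal correlation 0.5/0.7/0.9, with the Bonferroni procedure succeeding if any day passes 0.05/7:

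| True effect | Week mean | Bonferroni over 7 days |
|---|---|---|
| 0.464 SD on all days | 96/90/83% | 91/83/72% |
| 0.464 SD on first 3 days only | 36/29/24% | 81/75/67% |

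At the first step of a Holm procedure over the two enzymes (0.025), the week-mean figures in the second row fall to 26/20/16%. Under AR(1), at 0.05, the second row is 53/39/27% against 82/77/68%. The Bonferroni daily procedure keeps its false-positive rate at or below 4.5% per enzyme.

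**4. What a bare P value leaves open.** The 95% half-width for a single-day comparison is 1.976 × 0.1644 = 0.325 SD. For the t test, the P value fixes the size of the observed difference as t(1 − p/2) × 0.1644. The further confidence limit is that value plus 0.325:

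- p = 0.30: 1.040 × 0.1644 + 0.325 = 0.496 SD
- p = 0.50: 0.436 SD
- p = 0.90: 0.346 SD

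So only P values between about 0.05 and 0.30 leave a 0.5 SD effect inside the interval. That imprecision comes from the sample size and would be the same if the plan had named a day.

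**The case for a change.** The strongest case for a change is that the freedom is wide, it concerns the first-listed outcome, and it costs very little to remove. A few sentences naming one comparison per enzyme and asking for estimates with intervals would do it, with no new data. Where several compliant analyses can disagree, a reader cannot tell afterwards whether the reported one was picked for its result.

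Part of this stands. The plan is silent, and a report that gives every day's difference with its interval, or says plainly which summary was compared, is easier to trust than a selection of P values.

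The rest is weaker. The plan does not say that each day is tested, and does not say that one significant day would be taken as a positive result. Silence on intervals does not mean they will be left out. Nor does the document say whether an effect would last the week or be brief, so it gives no ground for preferring a week mean to a peak, an area under the curve, a named day or an error-controlled daily analysis. Finally, the Participants section already gives the analysed numbers and drop-outs, and the analysis paragraph is in the past tense. If the arms have been compared, a summary named now would be post hoc and would not provide the protection for which it is wanted.

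**Conclusion.** No change follows. The gap is one of detail: the tests named are valid for any per-donor value under randomisation, and nothing in it biases the comparison. The inflated error of 11-27% per enzyme describes one possible misuse under assumed correlations of 0.5-0.9, not something the plan prescribes. Imposing one particular summary is a trade-off. With equal correlation, the week mean gains 5 to 11 percentage points over Bonferroni daily testing for a constant 0.464 SD effect (96 − 91 = 5, 83 − 72 = 11). It loses 43 to 46 points if that effect is confined to the first three days (67 − 24 = 43, 81 − 36 = 45, 75 − 29 = 46). An analyst can sensibly show all days or compare one stated summary, and either is consistent with the text.

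This rests on seven measurements per enzyme, two-sided tests, equal SDs across days and the assumed correlations. It would change if the document said that any significant day is to be read as an effect, which it does not. The conclusion covers AST and ALT only, not the liver regeneration index or delayed recovery of hepatic function.
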